### 10.1.2 Visit windows

For visit-based variables (for visits see schedule of assessments in [Table 1](#) and [Table 2](#)), analysis windows are based on study day numbers defined as follows:

**Study day** is defined for the entire study as assessment date minus randomization date plus 1 day. Thus, the day of randomization is study Day 1. For dates prior to randomization, study day is the negative number of days between the date under consideration and the date of randomization. Thus, the day before randomization date is study Day –1. Study Day 0 does not exist.

**Withdrawal (WD)** day is defined for the DB-WD part as assessment date minus re-randomization date plus 1 day. If a subject is not re-randomized, then WD day is not defined.

The analysis windows around the visits are given in [Table 6](#). For efficacy variables (except for ABPM measurements) and safety analyses the windows are based on study or WD days and on the start and stop dates of the study parts defined above.

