**Table 6 Visit windows**

Visit	Target		Efficacy		Safety	
	Study day	WD day	Lower a	Upper a	Lower a	Upper a
DB part						
4 (Randomization)	1	-		1		1
5 (Week 2)	14	-	8	20	2	20
6 (Week 4)	28	-	21	36 b	21	36 b
SB aprocitentan part						
7 (Week 6)	42	-	37 c	62	37 c	62
8 (Week 12)	84	-	63	111	63	111
9 (Week 20)	140	-	112	167	112	167
10 (Week 28)	198	-	168	223	168	223
11.1 (Week 36)	252	-	224	258 d	224	258 d
DB-WD part						
11.2 (Re-randomization)	-	1		1		1
12 (Week 38)	266	14	8	20	2	20
13 (Week 40)	280	28	21	41	21	41
14 (Week 44)	308	56	42	69	42	69
15 (Week 48)	336	84	70	97	70	97 e
EOS (EOT + 30 days)	366	114	NA	NA	98	

a vs study day for the DB part and vs WD day for DB-WD part. b Or end of DB treatment part + one day (whichever comes first). c But not before start of SB aprocitentan part (whichever comes first). d Or end of SB aprocitentan part + one day (whichever comes first). e Or end of DB-WD treatment part + one day (whichever comes first).  
 DB = double-blind; NA=Not applicable; WD = withdrawal.

If there is more than one value within the same visit window, the value closest to the planned assessment date will be taken. Where multiple assessments fall on the same day or have the same visit label, then the latest in time is used (or with the highest SDTM sequence number, if time is not collected). In the event of equidistant values from the planned time point, the last assessment will be considered for the analyses. If there are records ‘on-treatment’ and ‘off treatment’ within the same visit window, use only those ‘on-treatment’.

If measurements involve time, the following target times should be considered:

- Target day/time = Target day and time 12:00
- Lower day/time = Lower day and time 0:00
- Upper day/time = Upper day and time 23:59

AOBPM measurements (efficacy) will also have indicator whether the measurement was ‘on-treatment’. A measurement is considered on-treatment if it was taken before or within one day of the end of the randomized treatment period (defined above).

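### Table 6 of the SAP sets the Week 28 target at study day 198 while Table 2 plans Day 196, so the closest-value rule can select a different, later record at that visit.

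*SAP*

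**What the plan says.** Table 2 of the SAP schedules Visit 10 (Week 28) at Day 196, with ±10 days. Section 10.1.2 numbers the days: "Thus, the day of randomization is study Day 1".

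Table 6 gives the targets and window limits. The Week 28 row reads "10 (Week 28) 198 - 168 223 168 223", that is, target 198 and window 168 to 223 for both efficacy and safety. The row before it is "9 (Week 20) 140 - 112 167 112 167". The row after it begins "11.1 (Week 36) 252", and its window opens at 224.

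Four rules under Table 6 decide which record represents a visit:

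- Closest value: "If there is more than one value within the same visit window, the value closest to the planned assessment date will be taken".
- Same day or same label: "Where multiple assessments fall on the same day or have the same visit label, then the latest in time is used".
- Ties: "In the event of equidistant values from the planned time point, the last assessment will be considered for the analyses".
- On-treatment records displace off-treatment records in the same window.

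For measurements with a clock time, the reference is "Target day/time = Target day and time 12:00".

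**The concern.** A target that is wrong in the selection table is an operative figure, because it decides which of two values enters a by-visit summary. Two values in one window are foreseen: sections 7.3.1, 7.4.1 and 7.5.1 put unscheduled assessments through these windows.

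The SAP also leaves open which day governs at Week 28. The closest-value rule speaks of the planned date, which Table 2 puts at Day 196. The clock-time rule refers to the target day, which Table 6 puts at 198. Two programmers working independently could each follow the SAP and still produce different Week 28 tables.

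**Working it through.** **Inputs.** Planned Day 196 ± 10 (SAP Table 2). Target 198, window 168–223, and neighbouring targets 140 and 252 (SAP Table 6). Selection and tie rules (text under Table 6). For affected sites, ±3 weeks for single-blind visits other than Visits 7 and 11 (addendum section 2.1.1).

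**1. Is 198 out of line?** The other ten week-labelled targets are Week 2 = 14, Week 4 = 28, Week 6 = 42, Week 12 = 84, Week 20 = 140, Week 36 = 252, Week 38 = 266, Week 40 = 280, Week 44 = 308 and Week 48 = 336. Each equals 7 × week and agrees with Table 2. For Week 28, 7 × 28 = 196, so the printed 198 is 2 days late. Counting from Day 1 does not explain it: adding one day would give 197, and no other row adds a day.

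**2. Which target produced the window?** The limits on either side of Week 28 are midpoints between adjacent targets.

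| Target | Boundary with Week 20 | Boundary with Week 36 |
|---|---|---|
| 196 | (140 + 196)/2 = 168 | (196 + 252)/2 = 224 |
| 198 | (140 + 198)/2 = 169 | (198 + 252)/2 = 225 |

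Table 6 opens Week 28 at 168 and Week 36 at 224. Only 196 reproduces both.

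**3. When does the choice change?** Take two values on days a < b, and target T. With ties going to the last value, b is chosen when a + b ≤ 2T.

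- T = 196: b is chosen if a + b ≤ 392.
- T = 198: b is chosen if a + b ≤ 396.

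The choices differ only when a + b is 393, 394, 395 or 396, and 198 then takes the later record. For example, Days 196 and 199 sum to 395. Target 196 keeps Day 196 (distances 0 and 3); target 198 takes Day 199 (distances 2 and 1). If one value is on Day 196, the choice changes only when the other is on Day 197, 198, 199 or 200.

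**4. How often?** Let a visit on day a be followed by a second value d days later. The choice changes when 393 ≤ 2a + d ≤ 396. These are four consecutive integers, so exactly two values of a qualify for any d: 196 and 197 for d = 1, 195 and 196 for d = 3, 190 and 191 for d = 14.

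- Visits even over Days 186–206 (21 days), d from 1 to 14: 2/21 = 9.5%.
- Visits even over 196 ± 21 = Days 175–217 (43 days): 2/43 = 4.7%. For d = 14, keeping both values inside 168–223 leaves visit days 175–209 (35 days): 2/35 = 5.7%.

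Counting day pairs equally instead, 104 of the 1,540 pairs in 168–223 change (6.8%), as do 36 of the 210 pairs in 186–206 (17.1%). These figures weight the days differently; none is an expected share of subjects.

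**The case against.** The strongest reply is that the closest-value rule names the planned date, not the Table 6 target, and Table 2 plans Day 196. On that reading 196 already governs and nothing goes wrong. The target-day line is stated for measurements with a clock time. This stands as a limit on the claim: the SAP offers two reference days, and the documents do not show that 198 will be used. It is still a reason to reconcile the tables.

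A reader might infer that the rule picks the wrong record whenever two values fall in the Week 28 window. The documents do not support that. Outside sums of 393–396 both targets choose the same record. Values under the same visit label go to the latest in time whatever the target, so in the Day 196 and Day 199 example a repeat labelled Visit 10 would be taken either way. The on-treatment preference can also decide before distance matters.

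A reader might also infer a bias toward repeats taken because a result was abnormal. The documents do not say why second values are taken. The shift favours the later record, which is the scheduled one if the extra value came first.

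The midpoint pattern is not universal: Weeks 4 and 6 are split at 36/37, where the midpoint is 35. It does hold at both edges of Week 28, and Table 2 and the 7 × week pattern lead to 196 without it. A 6 read as an 8 when a PDF is converted to text cannot be excluded; the signed SAP would settle that.

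**Conclusion.** The inconsistency is real and minor. Table 6 disagrees with Table 2 at Week 28, and 198 is the figure that fits neither the other targets nor its own window. Neither section 11 nor a Table 6 footnote marks it as deliberate.

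The effect is limited to pairs with study days summing to 393–396, on different days, under different visit labels, not already settled by the on-treatment preference, and processed with the Table 6 target. The share is 9.5% over Days 186–206 and about 5% under the addendum's wider window. Both shares assume evenly spread visit days and are conditional on a subject having two such values. The documents give neither the distribution of visit days nor the frequency of second values, so the number of subjects affected cannot be derived. Subjects with one value are unaffected, and no value changes window.

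The outputs exposed are Week 28 laboratory, weight and pulse summaries (descriptive), blood pressure control and response tables (tested only at Weeks 4 and 40), and the UACR mixed model (an other-efficacy analysis without multiplicity control). The primary analysis uses Weeks 2 and 4, and the key secondary uses Weeks 38 and 40 against the DB-WD baseline. Neither uses the Week 28 target.

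**What to change.** Change the Week 28 target in Table 6 from 198 to 196, in agreement with Table 2. Leave the window limits at 168 and 223. The cost is one number in the SAP and, if 198 was coded, one in the windowing program. No data collection, analysis model or clinical rule changes.

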 Study treatment including standardized background antihypertensive therapy should be brought back at each visit for drug accountability (pill counts).

 All AEs and SAEs that occur after signing the informed consent form and up to 30 days after study treatment discontinuation must be reported.

 Randomized subjects who prematurely discontinue prior to Week 48/Visit 15 should have an EOT visit scheduled no later than 7 days after the last dose of randomized study treatment.

 For subjects who discontinued during the RI period, this will be a phone call to collect adverse events and concomitant medications only.

ABPM = ambulatory blood pressure monitoring; AE = adverse event; AOBPM = automated office blood pressure measurement; BP = blood pressure; DB = double-blind; ECG = electrocardiogram; EOS = End-of-Study; EOT = End-of-Treatment; FU = follow-up; HR = heart rate; NT-proBNP = N-terminal pro-brain natriuretic peptide; PK = pharmacokinetic(s); RI = run-in; SAE = serious adverse event; SB = single-blind; UACR = urine albumin-to-creatinine ratio; WD = withdrawal.

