### **6.3.2 Intercurrent events and choice of estimand**

There are three types of intercurrent events that may interfere with the analysis of the key secondary endpoint: premature discontinuation of DB-WD treatment, initiation of antihypertensive rescue medication (in the DB-WD part) or the addition / dose increase of a diuretic (in the DB-WD part).

All AOBPM measurements, irrespective of any intercurrent event(s), will be included in the analysis, leading to a treatment policy strategy estimand in ICH terminology [[ICH 2017b](#)].

It is expected that 10% of subjects in the mFAS will have a missing Week 40 AOBPM. In the main analysis [Section 6.3.3] missing data will not be imputed but will be handled by a mixed model assuming that the missing data are MAR. Sensitivity analyses will be performed, investigating the impact of deviations from MAR as well as considering a different estimand [Section 6.3.4].

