### 6.3.4 Sensitivity analyses for the key secondary endpoint

The impact of deviations from the MAR assumption underlying the mixed model will be investigated in sensitivity analyses under MNAR as described in Section 6.2.4 and detailed in Section 8.2.

In another sensitivity analysis on the mFAS, all AOBPM measurements obtained *more than one day* after premature discontinuation of DB-WD treatment will be excluded from the main analysis. In addition, the initiation of antihypertensive rescue medication could influence the BP of a subject [O'Neill 2012]. For this reason, AOBPM measurements obtained after initiation of antihypertensive rescue medication in the DB-WD part will also be excluded from this analysis (i.e., considered as missing), leading to a hypothetical strategy estimand in ICH terminology [ICH 2017b]. Finally, AOBPM measurements taken after the addition of a diuretic (but also having an impact on BP) will be excluded from the analysis. (Note: antihypertensive rescue medication or a diuretic initiated in the SB aprocitentan part that is continued unchanged in the DB-WD part will *not* lead to exclusion from analysis).

Finally, the main analysis for the key secondary endpoint will be performed excluding site 4204 from which the data are considered not trustworthy (as per internal audit report).

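### The on-treatment-first rule in SAP Section 10.1.2 is not limited to any analysis, so for some subjects it selects a Week 40 reading that does not match the treatment-policy estimand of the key secondary endpoint

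*SAP*

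**What the plan says.** SAP Section 6.3.2 sets the main estimand for the key secondary endpoint: "All AOBPM measurements, irrespective of any intercurrent event(s), will be included in the analysis, leading to a treatment policy strategy estimand in ICH terminology". Premature discontinuation of withdrawal-part treatment is one of its three listed intercurrent events. Table 4 marks the main-analysis row Included for data after an intercurrent event.

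Dropping post-discontinuation data belongs to a sensitivity analysis. Section 6.3.4 says that readings obtained more than one day "after premature discontinuation of DB-WD treatment will be excluded from the main analysis", which gives the hypothetical strategy.

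The text below Table 6 in Section 10.1.2 has two rules for choosing among several records:

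- A general rule: "If there is more than one value within the same visit window, the value closest to the planned assessment date will be taken", with ties going to the later assessment.
- An override: when on-treatment and off-treatment records occur "within the same visit window, use only those" that are on-treatment. No analysis is named.

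Treatment status is defined there too: "A measurement is considered on-treatment if it was taken before or within one day" of the end of the randomized treatment period. With last dose on day x, day x + 1 is on-treatment and day x + 2 is off-treatment.

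In Table 6 the Week 40 efficacy window is withdrawal (WD) days 21 to 41 with target day 28. It carries no end-of-treatment footnote, unlike the Week 4 window (footnote b). Table 2 footnote 11 says that early discontinuers "should have an EOT visit scheduled no later than 7 days after the last dose of randomized study treatment", and AOBPM is scheduled at that visit.

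**The concern.** A treatment-policy analysis uses the outcome at the time point whether or not the subject is still on drug. The override chooses the record because of discontinuation, which is an intercurrent event that Section 6.3.2 says must not matter. In an affected subject the main analysis takes a reading from before or just after the last dose, although a later off-treatment reading nearer the target day exists.

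Two things are at stake. The test of the third null hypothesis, which is under alpha control, would rest partly on records that do not match its stated estimand. Also, in those subjects the main and hypothetical analyses would use the same value (unless an earlier rescue or diuretic change already excludes it from the latter), so comparing the two analyses would show less than it should about the effect of stopping.

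**Working it through.** The plan has no figure that depends on this rule. Its only power figure for the withdrawal part is 85% at 324 re-randomized (Section 2.1). It cannot be reproduced, because the documents supplied give no effect size or SD, and it does not bear on the question.

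**Inputs.** Window 21 to 41, target 28, ties to the later record (Section 10.1.2 and Table 6). On-treatment up to x + 1, off-treatment from x + 2 (same place). Visit 13 on day 28 ± 4, with the EOT visit within 7 days of last dose (Table 2). Planned 600 randomized and 380 re-randomized 1:1; 730 actually randomized (Section 2.1).

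**1. When can both kinds share the window?** An on-treatment reading needs x + 1 ≥ 21, and an off-treatment one needs x + 2 ≤ 41. So the last dose is on WD days 20 to 39. For each x there are x − 19 possible on-treatment days and 40 − x possible off-treatment days. Summing (x − 19)(40 − x) over x = 20 to 39 gives 1,540 day combinations.

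**2. When does the override change the record?** Let the on-treatment reading be on day a = 28 − k, with k = 1 to 7. The off-treatment reading on day b wins under closest-to-target when a < b ≤ 28 + k (b = 28 + k is the tie). For each pair, x can take b − a values. The count for each k is 1 + 2 + … + 2k = k(2k + 1), and the sum over k = 1 to 7 is 3 + 10 + 21 + 36 + 55 + 78 + 105 = 308. These have a on days 21 to 27, b on days 22 to 35, and last dose on days 20 to 33.

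**3. Scheduled visits only.** With Visit 13 on days 24 to 32 while on treatment, followed by EOT within 7 days of last dose, the record changes in 67 of 567 combinations: Visit 13 on days 24 to 27, last dose on days 23 to 30. These counts, like those in steps 1 and 2, are of possible day patterns, not shares of subjects.

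**4. Examples.**

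| Last dose | Readings (WD day) | Override selects | Closest-to-target selects |
|---|---|---|---|
| 24 | 24 (Visit 13), 28 (EOT) | 24 | 28 |
| 22 | 23, 28 | 23 | 28 |
| 30 | 28 (Visit 13), 36 (EOT) | 28 | 28 |
| 15 | 28 only | 28 | 28 |

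The first row conforms to the visit schedule. The last two rows are unaffected.

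**5. Size.** Shift in an arm mean per affected subject = difference between the two readings / subjects in the arm. Take 15 mmHg as an assumed difference.

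- Planned arm size: 380 / 2 = 190, so 15 / 190 = 0.079 mmHg.
- Scaled to actual randomization: 730 × 380 / 600 ≈ 462, or about 231 per arm, so 15 / 231 = 0.065 mmHg.

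The share affected is not in the documents. If it were 0.5% to 2% of an arm with differences of 5 to 15 mmHg (both assumed), the arm mean would move by 0.005 × 5 = 0.025 to 0.02 × 15 = 0.3 mmHg.

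**The case against.** The strongest defence is that the mixed model takes one record per subject and visit, so including all measurements cannot mean using every reading in a window. A Visit 13 reading on day 24 is within its allowed ± 4 days and is a legitimate Week 40 value. This is right as far as it goes, but the SAP already has a neutral way to choose one record. The override displaces it solely on treatment status, and that is the conflict.

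Several limits do stand:

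- A reader might infer that off-treatment Week 40 data are discarded in general. They are not: a subject with only off-treatment readings in the window keeps them, and nothing changes if the on-treatment reading is also the closest. Nor does the rule act on rescue or diuretic events while study drug continues, because treatment status depends only on the end of the randomized treatment period.
- A reader might infer a consistent bias towards aprocitentan. Section 6.2.4 anticipates that the BP effect is lost quickly after stopping. Keeping the on-drug value then favours aprocitentan when one of its subjects stops and starts nothing else. The sign can reverse: an aprocitentan subject who stops for lack of efficacy and starts another drug keeps the higher value, and a placebo subject whose BP is still rising keeps the lower one.
- A reader might take the sentence as a leftover from the former hypothetical main estimand. The revision history says only that Section 10.1.2 was changed and clarified in Version 3. It does not show whether this sentence was overlooked or kept on purpose.
- Cases built on unscheduled readings are less secure. The SAP expressly re-assigns unscheduled assessments to visits for laboratory, ECG and vital signs data, but has no matching statement for efficacy AOBPM.

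**Conclusion.** The contradiction is real and can arise through scheduled visits alone. Followed literally, Section 10.1.2 makes the treatment-policy main analysis at Week 40 use an on-treatment reading in place of one nearer the target day, for subjects with the pattern in step 2. The same sentence also acts on the Week 38 window, which enters the same model. At Week 4, footnote b already closes the window at treatment end plus one day, which is a separate matter.

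The expected effect is small, at about 0.065 to 0.08 mmHg on an arm mean per affected subject under the assumed 15 mmHg difference. The number affected is unknown, the net direction is not established, and nothing in the documents shows that the conclusion on the third hypothesis would change. The case for correcting it is that a confirmatory analysis should follow its stated estimand and that the correction is easy.

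**What to change.** In Section 10.1.2, limit the on-treatment-first sentence to the hypothetical-strategy analyses (Table 4 rows marked Excluded). For rows marked Included, select the record closest to the target day, ties to the later, regardless of treatment status. State which rule applies to the PPS and mPPS rows marked NA, which would otherwise have none.

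The cost is a short change to the SAP text and a flag in the windowing program; no new data are needed. Counting the subjects whose selected Week 40 record differs between the two rules would replace the assumed share with a known one.

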## 10.2 Handling of incomplete dates

In the following, ‘lower limit’ and ‘upper limit’ refer to the minimum or maximum, respectively, of a possible date. The ‘lower limit’ and ‘upper limit’ refer to the earliest and latest possible dates, respectively. As an example: if start date is ‘MAR2017’ (i.e., day missing), the lower limit is 01MAR2017 and the upper limit is 31MAR2017; if start date is ‘2017’ (i.e., day and month missing), the lower limit is 01JAN2017 and the upper limit is 31DEC2017. For time from first diagnosis of hypertension, take the lower limit.

### 10.2.1 Adverse events

The purpose of imputing AE dates is only to assign an AE to a specific treatment phase for the summary tables. No imputed date is considered in the medical evaluation of an AE. The imputation for incomplete AE dates is given in [Table 7](#).

**Table 7 Imputation rules for an incomplete or missing AE date**

Field	Incomplete date	Missing date
AE resolution date	The upper limit.	No imputation; the AE is considered as ongoing.
AE onset date	The below rule applies.  1.If the (imputed) resolution date is on or after the start of the <study treatment> and if the start of the <study treatment> falls within the upper and lower limits (inclusive), the <study treatment> start date is used  2. If the resolution date is missing and the <study treatment> start date falls within the upper and lower limits (inclusive) the <study treatment> start date is used  In all other cases the lower limit is used.	Whichever is the earlier of the date of resolution and the <study treatment> start date.

Depending on the analysis, <study treatment> is SB placebo, DB, SB aprocitentan or DB-WD treatment.

 If the randomized treatment period ends at study Day x then an AOBPM measurement taken at Day x + 1 will be ‘on treatment’, but a measurement taken at Day x + 2 will be ‘off-treatment’.

After applying the rules above, it may be that an AE can be allocated to multiple study parts. In that case, it will be allocated one study part according to the following priority: (1) DB part, (2) DB-WD part, (3) SB aprocitentan part and (4) RI period.

